In addition, we will monitor study subjects for any potential adverse events that may result from the use of corticosteroids. Although no significant complications were reported in the uncontrolled clinical reports of corticosteroids as adjuvant treatment of biliary atresia⁴⁶⁻⁴⁹, we will be particularly cognizant of the need to carefully monitor the subjects to determine the safety of the proposed treatment.

4.F. Study Design and Intervention

4.F1. Administration of Study Drug or Placebo

Written informed consent will be obtained either after a decision is made by the attending physician at the ChiLDREN site that the infant will undergo an exploratory laparotomy with possible portoenterostomy, or within 72 hours after portoenterostomy. As part of the informed consent, parents/legal guardians will be informed of potential side effects of corticosteroids, as well as of potential adverse consequences of the sudden discontinuation of high doses of corticosteroids (after use for more than 2 weeks). Some of the potential side effects of corticosteroid medications are listed below. This information will be shared with the subject's parents at the time of enrollment and are included in the "ChiLDREN corticosteroid information sheet", which will also be given to the subject's parents. The strategy to carefully monitor for the side effects is outlined in the Section 7.D.

- Hypertension
- Hyperglycemia
- Increased appetite, fluid retention, and weight gain

- Increased crying and decreased sleeping
- Increased risk of infection
- Impaired linear growth
- Cataracts
- Decreased response to immunizations
- Gastrointestinal bleeding
- Pancreatitis
- Hypokalemia
- Impaired wound healing

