We do not have data to present power calculations for the other secondary endpoints (sufficiency of fat-soluble vitamins and incidence of ascites). We do not anticipate sufficient deaths by age 2 to compare survival between treatment groups.

5.A.3. Tertiary Endpoints

Tertiary endpoints are those that may be affected by improved liver function. The hypothesis is that infants treated with corticosteroids will have improved liver function at 12 and 24 months of age, which will result in lower INR, higher serum albumin, lower PELD score, higher platelet count, higher serum sodium concentration, lower serum bile acid concentration, lower PIVKA-II, higher mid-arm circumference and triceps skinfold thickness, better HRQOL, improved neurodevelopmental outcome, and adequate immunologic response to childhood immunizations. However, the study is not powered to detect differences in these variables. Therefore, analyses of these data will serve to generate specific hypothesis for future studies.

5.A.4. Interim Analysis

There are both short-term (e.g., bilirubin at 6 months post-portoenterostomy) and long-term outcomes (e.g., survival with a native liver and developmental assessments at 12 and 24 months of age). Although there is a relationship between bilirubin at 6 months and survival with a native liver, the intervention may impact these endpoints differentially and, especially, may impact development and growth in a manner independent of the level of bilirubin at 6 months. Therefore, the Steering Committee recommends that the trial should not be terminated early based on a test for either efficacy or futility. The Steering Committee recognizes that the DSMB will monitor adverse events and may recommend ending the study early if there is a significant imbalance in adverse events (risk to the participants) between the two treatment arms.

5.B. Data Analysis

General

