Uncontrolled clinical trials of corticosteroid therapy following portoenterostomy in infants with biliary atresia reported collectively over 75 subjects with biliary atresia and over 100 episodes of corticosteroid treatment⁴⁶⁻⁴⁹. Regimens have included varying doses, durations, and times following portoenterostomy; no serious complications were reported. Adverse events in these studies, however, may not have been identified because of the small number of subjects included in individual studies or because adverse events may not have been systematically documented. Therefore, to monitor for potential adverse effects appropriately, we will systematically monitor all subjects at each scheduled visit. Subjects will be followed until complete/adequate resolution of an adverse event is documented. We will continue the evaluation of adverse events if a subject withdraws or is prematurely discontinued from participation in the study for any reason. The list of potential expected adverse effects was developed based on information from a pharmacology textbook and reviews of the published results clinical trials of dexamethasone to prevent chronic lung disease in over 1000 very-low-birth weight premature infants⁴⁵. Notably, some of the potential adverse effects of corticosteroids may also be present in infants with biliary atresia due to the natural progression of disease to biliary cirrhosis, such as gastrointestinal bleeding, growth impairment, and impaired response to routine immunizations. Therefore, it is important in this study that the frequency, severity and types of adverse effects, AEs and SAEs be compared between infants receiving study drug and those receiving placebo.

7.B2. Grading of AEs

An AE is any unfavorable or unintentional sign (including abnormal laboratory findings), symptom, or disease temporally associated with the use of a medicinal product, whether or not considered related to the medicinal product. Grading of AEs will be based on the National Cancer Institute-Common Terminology Criteria for Adverse Events⁷⁷⁻⁷⁹. Severity of AEs is outlined below:

- Grade 1: Mild adverse event
- Grade 2: Moderate adverse event
- Grade 3: Severe adverse event
- Grade 4: Life-threatening or disabling adverse event
- Grade 5: Death related to adverse event

7.B3. Serious Adverse Events (SAE)

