In this study, an SAE is defined as any clinical adverse event or abnormal laboratory test value that is associated with events that could threaten a subject's life or functioning,

irrespective of the study arm (corticosteroids or placebo) to which the subject was assigned. The term SAE is not intended as a measure of severity or intensity⁷⁷⁻⁷⁹. Thus, an AE should be considered a SAE if it results in any of the following:

- Death
- Is life-threatening (subject was at risk of death as a result of the event; it does not refer to hypothetical risk of death if the event had been more severe)
- Requires insubject hospitalization or prolongation of an existing hospitalization
- Results in persistent or significant disability/incapacity
- A congenital anomaly/birth defect
- Is medically significant or requires intervention to prevent one or other of the outcomes listed above

7.C. AE and SAE Reporting Plan

An investigator from the DCC will serve as the Medical Safety Officer. He/she will carry a pager so that all SAEs may be reported promptly. The DSMB will review all AEs and SAEs during their regularly scheduled meetings, or on an expedited basis as determined by the NIDDK Program Director or Chair of the DSMB, according to the ChiLDREN policy manual.

All unexpected adverse events (UAEs) are reported to the DCC by completion of the Adverse Events Form by the study site into the secure ChiLDREN website. This triggers an email message to the Medical Safety Officer to check the website for the report; no personal identifying or medical information is contained in the email message.

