All SAEs as defined previously require expedited event notification within 24 hours of occurrence or identification to the DCC. Expedited event notification is completed through web entry of the Adverse Events Form. Web entry generates an immediate email to the Medical Safety Officer with only the subject identification number in the message. The Medical Safety Officer then logs into the secure website to see the report of the event. In addition to web entry of the SAE, the Medical Safety Officer may be contacted for any questions or clarifications regarding classification of the event. Paging the Medical Safety Officer is not required as part of the expedited notification process, however may be used if any difficulty is encountered in the web-based notification system. Completing the web entry of the AE form will automatically send e-mail notification to the Medical Safety Officer, NIDDK Program Director, DCC PI, and Project Manager. Fax cover sheets are provided if there is a need to fax supporting information per request of the Medical Safety Officer or NIDDK Program Director. Once the Medical Safety Officer reviews the information submitted on the AE form, the clinical site will be contacted if additional information is required in order to draft a preliminary report of the SAE. Once completed, the preliminary report will be sent to the, the report will then be sent to the NIDDK Program Director, clinical site PI, DCC PI, Project Manager, and Chair of the DSMB.

Once the SAE is resolved, a final report is generated by the Medical Safety Officer. The Medical Safety Officer will send the final report to the NIDDK Program Director, clinical site PI, and the DCC PI and Project Manager. All SAE reports will go the DSMB for review. The NIDDK Program Director and the Chair of the DSMB will decide if any individual SAE

warrants notification to the FDA and to the IRB's of all participating ChiLDREN clinical sites.

The clinical site at which the SAE occurred is responsible for expedited reporting of the SAE to their respective IRB. Each site is responsible to report all AE's to their IRB according to its AE reporting policy and procedures.

Updates to SAEs are submitted to the DCC through web entry of AE form. An update report is generated through the same process that the original SAE report was entered. Updates to the AE form should be made until an outcome and end date for the event are known or if study participation ends.

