A random plasma glucose level will be obtained at the time of discharge and at follow-up visits (Table 6). If the random plasma glucose level is 200 mg/dL or higher the study subject will return within 24 hours for a repeat level. If the repeat glucose level is 200 mg/dL or higher⁸¹, a moderate AE will be reported and the study medication dose-reduction protocol (Section 4.F2) will be followed if the subject is asymptomatic. Persistent hyperglycemia above 200 mg/dL beyond 48 hours of dose reduction and associated with acidosis or change in mental status due to elevated serum osmolality will be considered a SAE, and the drug or placebo will be tapered and discontinued (Section 4.F3). If blood glucose is 150-200 mg/dL, treatment or observation will be directed by the local standard of care, including the option for study medication dose reduction (Section 4.F2).

7.D3. Hypokalemia

A random serum potassium level will be obtained at the time of hospital discharge and at follow-up visits (Table 6). If the potassium level is less than the lower limit of normal but above 3.0 mmol/L, a mild AE will be reported. A new serum K level will be obtained in 48 hours. If the potassium level is less than 3 mmol/L but \geq 2.5 mmol/L, a moderate AE will be reported and appropriate replacement therapy will be initiated. Repeat serum potassium levels will be obtained at 24 and 48 hours after start of replacement. If the levels do not normalize and the subject is asymptomatic, increased replacement will be initiated and the subject will be monitored closely. The clinical site PI will have the option to initiate study medication dose reduction (Section 4.F2). If the potassium is less than 2.5 mmol/L, a SAE will be reported, replacement therapy will be given immediately, and the study drug or placebo will be tapered and discontinued (Section 4.F3), unless another cause is identified as the cause for the hypokalemia (such as use of furosemide or another diuretic that may be used because of progression of liver disease and development of ascites).

7.D4. Impaired Wound Healing

Impaired wound healing is defined as a situation in which any of the following conditions are met:

- Readmission due to wound healing complications after discharge following portoenterostomy,
- Delay in discharge due to wound healing complications after portoenterostomy,
- Wound infection after portoenterostomy that requires specific treatment with antibiotics

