- Return to the operating room in less than 30 days for wound management.
- A late complication in wound healing following portoenterostomy, such as, ventral hernia, ascitic leak, etc

Wound healing will be assessed daily in the hospital after portoenterostomy by the clinical team. A formal evaluation by the clinical site PI and study coordinator will occur on the day of discharge and at weeks 2 and 4 after portoenterostomy. Delay in discharge or readmission due to wound healing complications after surgery will be reported as an SAE. Wound infection that requires specific treatment with intravenous antibiotics will also be reported as a SAE. At outpatient study visits, an assessment will be made as to whether there is adequate wound healing. If there is a wound infection requiring surgical intervention in the operating room (i.e. reoperation) or complete wound dehiscence, it will be reported as a SAE. In the event of any SAE, drug or placebo will be tapered and discontinued (Section 4.F3). Care of the subject for impaired wound healing will be done according to local standard of care.

7.D5. Gastrointestinal Bleeding

If hematochezia, melena, hematemesis, or visible blood through nasogastric or gastrostomy tube is reported, an evaluation of gastrointestinal bleeding will be performed (e.g., to rule out anal fissure, infectious colitis, allergic colitis). If the bleeding is not associated with a drop in hematocrit and no further evaluation is indicated, a mild AE will be reported. If the presence of hematemesis, hematochezia or melena is associated with a drop in hematocrit of >5%, a moderate AE will be reported and further evaluation will be considered as clinically indicated; the clinical site PI will have the option to initiate study medication dose reduction (Section 4.F2). If a packed red blood cell transfusion is required and/or endoscopic intervention (such as sclerotherapy) is necessary, this will be reported as a SAE. The presence of a hemoglobin level < 6.5 g/dl or systemic hypotension caused by acute gastrointestinal bleeding will also be reported as a SAE, and the study drug or placebo will be tapered and discontinued (Section 4.F3).

7.D6. Pancreatitis

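### Section 7.C's general rule for sending non-serious events to the DCC covers only unexpected AEs, which falls short of the AE review and between-arm comparison planned elsewhere

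*Protocol*

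**What the plan says.** Protocol 7.C sets two general routes from site to DCC. For serious events, "All SAEs as defined previously require expedited event notification within 24 hours of occurrence or identification to the DCC", whether expected or not. For other events the rule is "All unexpected adverse events (UAEs) are reported to the DCC by completion of the Adverse Events Form by the study site". No sentence in 7.C covers expected non-serious events in general.

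Four places rely on AE data without limiting it to unexpected events:

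- 7.C: "The DSMB will review all AEs and SAEs during their regularly scheduled meetings".
- 7.B1 calls it important that "the frequency, severity and types of adverse effects, AEs and SAEs be compared between infants receiving study drug and those receiving placebo".
- 5.A.4: the DSMB "may recommend ending the study early if there is a significant imbalance in adverse events".
- Section 8: the DSMB receives a quarterly cumulative AE summary, overall and by seriousness.

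The AE definition in 7.B2 makes no reference to expectedness.

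**The concern.** A steroid trial in infants has a long list of known drug effects, and 4.F1 sets them out in advance. If the general rule asks sites to send unexpected events, known effects reach the DCC only where some other section says so. Any that lack such a section would be incompletely recorded, although they are the effects for which a difference between arms is most plausible. The AE counts given to the DSMB and the final AE comparison would then partly reflect which events a site regarded as expected. 7.B1 itself warns that earlier steroid reports may have missed adverse events for want of systematic documentation.

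**Working it through.** No formula applies, and the protocol gives no figure to reproduce. The check is to match each of the 12 effects listed in 4.F1 to a reporting or measurement route.

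**Step 1. Is there a wider general rule elsewhere?** Two sentences look like candidates. Near its end, 7.C makes each site responsible for reporting all AEs to its own IRB under local policy. That report does not go to the trial database. Section 8 says AEs are reported as set out earlier, which leads back to 7.C and 7.D. Neither widens the rule.

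**Step 2. Match the 12 effects.**

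| Effect in 4.F1 | Route found |
|---|---|
| Hypertension | 7.D1 |
| Hyperglycemia | 7.D2 |
| Hypokalemia | 7.D3 |
| Impaired wound healing | 7.D4, in part |
| Gastrointestinal bleeding | 7.D5 |
| Pancreatitis | 7.D6 |
| Crying and sleep | 7.D7, severe irritability only |
| Cataracts | 7.D9 |
| Infection | 4.O3 and Table 8 |
| Linear growth | Secondary outcome |
| Vaccine response | Tertiary outcome |
| Appetite, fluid retention, weight gain | No AE rule; weight, edema and ascites examined at visits |

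Eight effects have a 7.D section and four do not (8 + 4 = 12). Of those four, infection has its own AE rules, and growth and vaccine response are measured in both arms. That leaves one listed item with no AE rule at all, "Increased appetite, fluid retention, and weight gain", and one covered only at its severe end (crying and sleep).

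**Step 3. Other routes for what is left.** Under 4.F2, any dose reduction is reported to the DCC together with the event. Under Table 8, emergency visits and hospitalizations are AEs. Under 7.C, anything meeting the SAE definition is reported. The gap is therefore limited to cases that are non-serious, involve no dose reduction and lead to no emergency visit.

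**Step 4. Look inside 7.D4.** The definition of impaired wound healing has five conditions. One is "Wound infection after portoenterostomy that requires specific treatment with antibiotics". The matching reporting sentence is narrower: "Wound infection that requires specific treatment with intravenous antibiotics will also be reported as a SAE". Two kinds of case fall between definition and report:

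- A wound infection treated without intravenous antibiotics. After discharge, 4.O3 may catch it, since an acute infectious illness leading to a primary care visit requires an AE form. If it is found and treated at a study visit, or in hospital without delaying discharge, no rule clearly applies.
- A late complication, such as a ventral hernia or ascitic leak, without readmission. It is in the definition, but no reporting sentence in 7.D4 reaches it unless it meets the SAE definition, for example as medically significant.

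**Result.** The events with no stated AE-form route are increased appetite, fluid retention as an AE, decreased sleeping, crying short of severe irritability, and those two kinds of wound case.

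**The case against.** The strongest reply has four parts.

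1. The word only is not in 7.C. The sentence says what is done with unexpected events and does not forbid entering expected ones. This is true, but it leaves expected events without an instruction. A reporting plan that feeds a DSMB review of all AEs needs one.
2. Absence of an AE form is not absence of data. Weight, skinfold thickness, edema and ascites are examined at each visit, and the case report forms collect diet, interval history and illnesses in both arms. This stands for weight and largely for visible fluid retention. It does not yield a graded AE count, and it does not specifically address sleep or milder crying.
3. The effects that 7.B1 names as overlapping with the disease (bleeding, growth impairment and vaccine response) are all captured. This also stands.
4. Site staff are blinded and the expected effects are listed in advance, so classification is not made knowing the arm. This weakens any claim of a directed bias.

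A reader might infer that every known steroid effect without a 7.D section drops out of the safety data. The documents do not support that: infection, growth and vaccine response have no 7.D section and are all captured. A reader might also infer that the comparison is shown to be biased toward no harm, or try to put a number on the loss. The protocol gives no rates for these events, so neither follows.

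The Adverse Events Form, the network policy manual and the manuals of operations are not shown, and they may ask for expected events. If so, practice is better than the protocol text, and the text should still be brought into line.

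**Conclusion.** The inconsistency is real and its reach is limited. Read as written, 7.C does not supply the AE data that 7.B1, 5.A.4, section 8 and 7.C's own DSMB sentence call for. The exposed events are mild or moderate, expected, and without a route in 7.D, 4.O3, Table 8 or 4.F2. They are one of the 12 listed effects as an AE (weight itself being measured), the milder end of a second, and part of a third, wound healing.

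If such events were more frequent on steroid, leaving them out would shrink the observed difference in AEs. Whether that happens, and by how much, cannot be estimated from the documents. SAEs, the events graded and reported under 7.D, infections and the outcome measures are not affected. The conclusion assumes that sites follow the protocol text and that no unseen form or manual sets a wider rule.

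**What to change.** In 7.C, require all AEs, expected or unexpected, to be entered on the Adverse Events Form, and use expectedness only to decide expedited notification. In 7.D4, state that each of the five listed conditions is entered at least as an AE, leaving the existing SAE criteria as they are. Check that the form instructions and manual of operations say the same.

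The cost is a short wording amendment, a revised instruction to sites, and somewhat more AE data entry. No dose, treatment or stopping rule changes.

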The Medical Safety Officer will submit an expedited report to the FDA of an SAE when the SAE is unexpected and may be related (even remotely) to the study drug.

7.D. Monitoring and Management for Specific AEs

Several side effects of corticosteroids are anticipated in the subjects randomized to corticosteroid treatment. The following section outlines the plan for monitoring and management of these AEs. This monitoring will be conducted after portoenterostomy however before the first dose of study medication is given (to provide baseline data) and then at hospital discharge and at each scheduled follow up visit.

7.D1. Hypertension:

If a significant hypertension (systolic blood pressure ≥ 112 mmHg for infants <12 months of age)^{80a,b,c} is measured at least two times, and the subject is asymptomatic, a repeat blood pressure will be obtained within 24-48 hours. If the elevated blood pressure is resolved, no intervention will be necessary. If the repeat systolic blood pressure is ≥ 112 mmHg and the subject is asymptomatic, the study medication dose-reduction protocol (Section 4.F2) will be followed and a repeat blood pressure will be obtained within 48 hours; a mild AE will be reported⁷⁷. If the repeat systolic blood pressure remains ≥ 112 mmHg but the subject remains asymptomatic, anti-hypertensive monotherapy will be initiated (see below). If the hypertension persists beyond 48 hours, a second dose-reduction will be initiated and a second anti-hypertensive medication may be used (see below). If hypertension does not resolve within 48 hours or if the subject develops symptoms due to hypertension (e.g.: severe irritability, seizure) or as other life-threatening consequences, such as end-organ damage, drug or placebo will be tapered and discontinued (Section 4.F3), the subject will be referred to an emergency department, and additional anti-hypertensive treatment will be initiated. This will be reported as a SAE.

- a. Treatment choices for hypertension with BP ≥ 112 mmHg without symptoms
- Hydrochlorothiazide: 2 mg/kg/day given once or twice a day, or
 - Amlodipine: 0.2-0.4 mg/kg/day given once or twice a day, or
 - Captopril: 0.3-1 mg/kg/day given twice a day
 - Other site-specific treatment choice

b. Treatment choices for hypertension with BP \geq 112 mmHg with symptoms

- Nifedipine 0.25-0.5 mg/kg/ sublingual
- Labetolol: 1-3 mg/kg/hour IV
- Other site-specific treatment of choice

7.D2. Hyperglycemia

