Because a single diagnostic test for pancreatitis is not available, a combination of tests and the best clinical judgment of the local PI will be used when evaluating the subject for possible pancreatitis. If there is new onset irritability presumed due to abdominal discomfort, progressive abdominal distension, inability to feed and/or vomiting, a serum lipase and/or pancreatic ultrasound will be ordered. If serum lipase is elevated (three times above the upper limit of normal) or ultrasound findings of pancreatitis are present⁸², this will be reported as a moderate AE; the clinical site PI will have the option to initiate study medication dose reduction (Section 4.F2). If the symptoms persist or require narcotic pain medication, or are associated with a pancreatic pseudocyst, hypocalcemia or anemia felt to be secondary to hemorrhagic pancreatitis, a SAE will be reported, and drug or placebo will be tapered and discontinued (Section 4.F3).

7.D7. Irritability

The development of severe irritability in the subject without an obvious cause will be considered a moderate AE, defined as the presence of inconsolable, persistent crying without an apparent cause, which requires evaluation and confirmation by the primary care provider or a visit to an emergency department if the subject is being followed as an outsubject, or by the clinical insubject team if the subject is in hospital at the time of the

event. Following evaluation for irritability and if no obvious cause is identified, a 50% dose reduction of study drug or placebo (Section 4.F2) will be considered by the clinical site PI. If the irritability resolves on this reduced dose, the duration of reduced dose will be the same as for the original dose, and the subject will continue to follow the remainder of the scheduled study drug/placebo regimen. The Medical Safety Officer will monitor all decreases in dose by clinical centers. If severe irritability persists despite the decrease in dosage, the study drug/placebo will be reduced by an additional 50%. If severe irritability persists despite this new reduction in dosage, the subject will undergo the tapering protocol and discontinuation of the study drug/placebo (Section 4.F3).

7.D8. Hypersensitivity Reaction to Trimethoprim-Sulfamethoxazole

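### Section 7.D1 gives asymptomatic hypertension no grade above mild until it becomes an SAE, and 7.D7 fixes severe irritability as moderate, so the severity comparison in 7.B1 may understate both

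*Protocol*

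**What the plan says.** Section 7.B2 bases AE grading on the NCI criteria and lists five grades: mild, moderate, severe, life-threatening or disabling, and death. Section 7.B1 calls it important that "the frequency, severity and types of adverse effects, AEs and SAEs be compared between infants receiving study drug and those receiving placebo". Section 7.B3 defines an SAE by its consequences and says that the term is not a measure of severity.

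Section 7.D then attaches labels event by event. For hypertension (7.D1), once a repeat systolic pressure is still at or above 112 mmHg in an asymptomatic infant, dose reduction follows and "a repeat blood pressure will be obtained within 48 hours; a mild AE will be reported". If pressure stays high, one antihypertensive drug is started. If it persists further, "a second dose-reduction will be initiated and a second anti-hypertensive medication may be used". The last step begins "If hypertension does not resolve within 48 hours or if the subject develops symptoms due to hypertension" and closes with "This will be reported as a SAE".

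For glucose at or above 200 mg/dL on repeat (7.D2), "a moderate AE will be reported and the study medication dose-reduction protocol (Section 4.F2) will be followed if the subject is asymptomatic". For irritability (7.D7), "The development of severe irritability in the subject without an obvious cause will be considered a moderate AE".

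**The concern.** Hypertension is the first-listed corticosteroid side effect in both 4.F1 and 6.A5b. It is also the 7.D event with the longest sequence of treatment steps short of an SAE. Yet the only severity word in 7.D1 is mild, and it is attached before any antihypertensive drug is given. An infant who settles after one dose reduction and an infant who needs two dose reductions and one or two drugs have the same stated grade. Elsewhere in 7.D the dose-reduction step is moderate.

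In 7.D7 the event is called severe in the text and graded moderate in the same sentence, and no other grade is stated even when study drug is stopped.

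What is at stake is the severity part of the comparison in 7.B1, and through it the risk-benefit analysis promised in 6.D. The label is assigned at data collection, so a later analysis plan cannot restore a grade that was not recorded.

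**Working it through.** No figure in the protocol is to be reproduced and no formula applies. The check sets the passages side by side.

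**Grade at the step where dose reduction enters**

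| Section | Event at that step | Dose reduction | Stated grade |
|---|---|---|---|
| 7.D1 | Systolic pressure at or above 112 mmHg on repeat, asymptomatic | required | mild |
| 7.D2 | Glucose at or above 200 mg/dL on repeat, asymptomatic | required | moderate |
| 7.D3 | Potassium below 3 but at least 2.5 mmol/L, not normalizing on replacement | optional | moderate |
| 7.D5 | Bleeding with a hematocrit drop above 5% | optional | moderate |
| 7.D6 | Raised lipase or ultrasound findings | optional | moderate |
| 7.D7 | Severe irritability without obvious cause | considered | moderate |

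Five of the five other events with both a stated grade and a dose-reduction step are moderate there; hypertension alone is mild. The closest pair is 7.D1 and 7.D2, which use the same wording to require dose reduction but give different grades. Two places fall outside the count. Glucose of 150-200 mg/dL allows dose reduction but has no stated grade, and wound healing (7.D4) has no dose-reduction step.

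**Grade along the 7.D1 sequence**

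1. First dose reduction: mild.
2. First antihypertensive drug: no grade stated.
3. Second dose reduction, second drug optional: no grade stated.
4. Unresolved within 48 hours, or symptoms or end-organ damage: SAE, no grade stated.

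Two steps lie between the mild report and the SAE. By 7.B3 the SAE step classifies seriousness, not severity, so 7.D1 states no grade above mild anywhere. The infants affected are those without symptoms whose hypertension resolves at step 2 or 3.

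**Contrast with 7.D3.** There, mild goes with a recheck and moderate with the start of replacement treatment. Drug treatment in 7.D1 brings no such change of grade.

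**Grade in 7.D7.** The label is moderate at onset. No other grade is stated at the first dose reduction, the second, or discontinuation, and 7.D7 itself has no SAE step. The severe grade in 7.B2 is not used.

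**Size.** The shift in the severity distribution depends on the hypertension rate in each arm, the share of infants reaching steps 2 and 3, and the share of sites that regrade. The protocol gives none of these.

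**The case against.** The strongest reply is that silence is not prohibition. Mild is attached at one point in time, 7.D1 cites the NCI criteria for it, and 7.B2 puts AE grading under those criteria. Nothing says that the grade is frozen, or that 7.D displaces 7.B2. This stands in part: a site may regrade. But nothing in 7.D1 directs it to, and a specific reporting instruction is likely to be followed over a general one. The instruction in 7.C to keep the AE form current sits in the paragraph on SAE updates and speaks of outcome and end date, not grade. Some of the 14 sites may regrade and others not. Whether mild or moderate departs from the NCI criteria themselves cannot be judged here, because their content is not in the protocol.

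Several stronger readings are tempting and are not supported:

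- A reader might infer that hypertension stays mild however badly it goes. It does not: failure of the last non-serious step, or any symptoms, leads to an SAE report, and the second drug is optional.
- A reader might infer that no infant can ever be recorded with moderate or severe hypertension. That treats an unstated grade as a forbidden one.
- A reader might infer that the arm comparison is biased toward no harm. The rule is the same in both blinded arms, so AE frequency and SAE comparisons are intact. What may be lost is severity detail within the non-serious events. Suppose, purely as an assumption, that 10% and 3% of 70 infants per arm need antihypertensive drugs: 0.10 × 70 = 7 and 0.03 × 70 = 2.1, about 2. If none becomes an SAE, all nine still count as hypertension AEs, 7 v 2. Only a table of moderate-or-worse events would vary, from 0 v 0 with no regrading to 7 v 2 with full regrading to moderate or above. The protocol plans no such table and gives no basis for these rates.
- A reader might infer that the DSMB would be misled. The cumulative AE summary in section 8 is split by serious and non-serious status, not by grade.

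It is also true that treatment burden is partly recoverable. Dose reductions go to the DCC with the AE notification (4.F2), the Medical Safety Officer monitors dose decreases (7.D7), and a medication record is taken at every visit (Table 6). That limits the loss but does not supply a severity grade.

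**Conclusion.** The concern holds in a limited form. Section 7.D1 states mild at a required dose reduction and no higher grade for the drug-treated steps before the SAE. Section 7.D7 fixes severe irritability as moderate. Both fit poorly with the single scale in 7.B2, and 7.D1 also departs from the other five graded events in 7.D.

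If sites keep the fixed labels, the severity comparison in 7.B1 may understate non-serious, drug-treated hypertension and severe irritability, and grades will not be comparable across event types. This rests on the assumption that sites follow the stated label rather than regrade. The effect is confined to severity grading and its size cannot be computed from the protocol. It is worth correcting because the severity comparison is an explicit aim and the correction is cheap.

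**What to change.** Remove the fixed mild label from 7.D1 and the fixed moderate label from 7.D7. State that each of these events is graded on the 7.B2 scale at the highest severity reached, and that the AE form is updated as the event evolves, for non-serious events as well as SAEs. Report SAE status separately from grade, as 7.B3 implies. Use the dose-reduction reports and medication records already collected to show action taken by arm, alongside the grade. Leave all management steps in 7.D as they are.

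The cost is about two sentences in 7.D and a note on completing the AE form. It needs no new data item and no change in care. The downside is slightly more effort at sites to keep grades current.
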